ID: IB2019-METAGIST

Patterns of Care and Outcomes of Patients With METAstatic Gastrointestinal Stromal Tumors (METAGIST)

NCT03963544

Sept 1, 2018

Title	
METAGIST
 
Patterns of care and outcomes of patients with METAstatic GIST in a real-life setting: the METAGIST national observational study from the GSF-GETO

Rational	
Gastro intestinal stromal tumors (GIST) are rare mesenchymal tumors of the gastrointestinal tract characterized by somatic mutations in the gene encoding the KIT or the PDGFR alpha protein. Treatment of localized forms relies on adequate surgery without tumor spillage and systemic treatment with imatinib according to risk of relapse defined by localization, tumor size and mitotic count, as well as mutational status. Advanced and relapsing forms are currently treated with oral tyrosine-kinase inhibitors (TKI) of KIT and PDGFR such as Imatinib, Sunitinib and Regorafenib. Over two decades significant changes in drug discovery have impacted treatment strategies, notably via patient's access to various clinical trials. The use of focal treatments such as surgery or interventional radiology with mini invasive procedure of oligometastasis is also being proposed in some cases.
 
There is no precise data on patterns of sequential treatments used, especially proportions of patients with metastatic GIST eventually benefiting from access to a clinical trial or a focal treatment strategy in the course of their disease, and their results in terms of survival on a real life national level.
 
Using the French sarcoma Group national database we aim at describing treatments strategies proposed patients with metastatic GIST in the real life setting.

Objectives	
Primary objective
 
To describe clinic-biological profiles, patterns of care and modalities of treatment of patients with metastatic GIST in a real-life national setting.
 
Secondary objectives
 

- time to next treatment (TNT)

- overall survival

- proportion of patients included in a clinical trial during the course of their disease

-

Material and Methods	
Inclusion
 
 
- patients <math>\geq</math> 18 years old
 
- with a diagnosis of metastatic GIST (metastatic at diagnostic or metastatic relapse)
 
- From 1990 to 2018
 
- with histological review performed by members of the pathological sub-committee of the GSF-GETO
 
- treated in one of the participating national reference network centers members of the GSF-GETO
 
- included in the prospectively maintained database of the GSF-GETO: the ConticaGIST
 
 
Methods
 
Descriptive data (see SARCOMABCB DICTIONNARY)
 
 
- Initial patients characteristics: age, gender, PS
 
- tumor characteristics : date, histology, location, size, mitotic count, miettinien classification, mutational status
 
- Initial treatment : initial surgery type, date, margins, tumor spillage, adjuvant systemic treatment (start and stop date)
 
- Metastatic disease characteristics : date, PS, location of metastasis
 
- Treatment in the metastatic setting : molecule used (start and stop date, best RECIST response), locoregional treatment performed, inclusion in a clinical trial
 
- Latest status : date, patient lastest Status, tumor latest status
 
 
Survival data
 
 
- Time to next treatment (TNT) TNT defined as the time from the systemic treatment onset to the next treatment or death due to any cause, whichever came first. When neither death nor new systemic therapy is observed, TNT is censored at the date of last patient contact.
 
- Overall survival in the metastatic setting (OS) defined as the interval between the diagnosis of metastatic disease or the first-line systemic therapy onset and the time of death. When death is not observed, OS is censored at the date of last patient contact.
 

Statistics	
Statistical analysis of the baseline demographics and clinical outcomes will be based on all data available up to the cut-off date of December 31, 2018. Descriptive statistics will be used to show the distribution of variables in the population. Multivariate logistic regression models will be used to identify biological and clinical factors associated with the type of treatment received and with the probability of survival 5 years after the diagnosis of metastases. Follow-up times will be described as median values based on the inverse Kaplan–Meier estimator. Prognostic factors of TNT and OS will be identified using Cox proportional hazard models. The variables included in the univariate and multivariate analyses are the descriptive data.

	The correlation between TNT and OS will be evaluated at each of the four first-lines of metastatic chemotherapy by a Spearman rank correlation coefficient and expressed as a value between 0 (no association) and 1 (perfect association). We will use a reviewed copula-based approach that introduces an iterative multiple imputation method for the estimation of the correlation coefficient. The data will be analyzed using the SAS v9.3 and R v3.3 software packages.
Timeline	February 2019 : end of collection of data and updating of the conticaGIST March - April 2019 : first version statistical analyses
Ref	
 
 
 
 

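### The share of patients with a trial inclusion by the cut-off is, within the registered cohort, only a lower bound for whole-course inclusion; label it so and, if dates allow, add a fixed-time cumulative incidence

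*Combined protocol and SAP*

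**What the plan says.** - **Objectives, Secondary objectives:** the target is the "proportion of patients included in a clinical trial during the course of their disease". No time point, denominator or estimator is given.
- **Rational:** the evidence gap is put in the same whole-course terms, "especially proportions of patients with metastatic GIST eventually benefiting from access to a clinical trial or a focal treatment strategy". The section also notes that "Over two decades significant changes in drug discovery have impacted treatment strategies, notably via patient's access to various clinical trials".
- **Material and Methods, Inclusion:** patients qualify "From 1990 to 2018", with no minimum follow-up. They must be treated in a participating reference centre and be in the group's database.
- **Material and Methods, Methods:** the items for the metastatic setting are "molecule used (start and stop date, best RECIST response), locoregional treatment performed, inclusion in a clinical trial". Molecules have dates; trial inclusion has no date of its own in this list. The dates of metastatic disease and of latest status are also collected. TNT and OS each have an explicit censoring rule.
- **Statistics:** the analysis "will be based on all data available up to the cut-off date of December 31, 2018". The only stated method that covers this proportion is general: "Descriptive statistics will be used to show the distribution of variables in the population". Median follow-up is to be reported by the reverse Kaplan–Meier method.

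**The concern.** The objective describes a completed disease course, but the data describe courses cut at one calendar date. Inclusion runs into the year of the cut-off, so potential follow-up ranges from almost nothing to 29 years (start of 1990 to end of 2018). A patient diagnosed with metastases in 2017, alive and not yet in a trial, counts as 'no' in a crude share just like a patient followed to death without one. The figure then depends on the mix of follow-up as well as on access to trials. The plan handles unfinished follow-up for TNT and OS, but gives this proportion neither a method nor a caveat.

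At stake is how a headline descriptive result is read, since the Rational names trial access as something on which precise data are lacking. An unlabelled percentage invites the reader to take it as whole-course access.

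**Working it through.** The documents give no expected proportion, sample size or survival figure, so there is no planned number to reproduce.

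**1. Direction.** Let *a* be the share of the cohort with a recorded inclusion by the cut-off, and *c* the share alive or lost and never in a trial. Then a ≤ eventual share ≤ a + c. For example, a = 20% and c = 30% give 20% to 50%. The crude share equals the eventual share only if none of the patients in *c* ever enters a trial.

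**2. Size, on assumed inputs.** From the documents: entry from 1990 to 2018 and cut-off at the end of 2018, hence 29 years. Assumed: eventual share 30%, exponential survival, no loss before the cut-off, and accrual either uniform or rising linearly. With F(u) the cumulative incidence of trial entry (death competing) at u years,

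crude share = ∫₀²⁹ F(u) g(u) du, with g(u) = 1/29 (uniform) or 2(29 − u)/29² (rising).

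- *Early entry, mean 1 year:* F(u) = 0.30(1 − e^(−u)).
- *Constant rate, median OS 5 years:* death rate ln 2/5 = 0.1386; total rate h = 0.1386/0.70 = 0.198; F(u) = 0.30(1 − e^(−hu)). Uniform accrual: 0.30 × [1 − (1 − e^(−29h))/(29h)] = 0.248.
- *No entry before year 3:* F(u) = 0.30(1 − e^(−k(u−3))) for u > 3. The share of 3-year survivors who later enter is 0.30/S(3), that is 0.30/0.660 = 0.455 (OS 5) or 0.30/0.771 = 0.389 (OS 8); k is the death rate divided by one minus that share.

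| Assumed pattern | Crude share, uniform / rising | Shortfall from 30%, points |
|---|---|---|
| Early entry | 29.0% / 28.0% | 1.0 / 2.0 |
| Constant rate, OS 5 | 24.8% / 21.4% | 5.2 / 8.6 |
| None before year 3, OS 5 | 22.8% / 17.9% | 7.2 / 12.1 |
| None before year 3, OS 8 | 19.8% / 14.5% | 10.2 / 15.5 |

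The largest value needs late entry, long survival and rising accrual together. Loss to follow-up widens the gap. In a separate constant-rate case (eventual share 35%, uniform accrual over 28 years, median survival 6 years), the crude share is 28.0% without loss and 23.0% with 5% lost per year.

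**3. Does a fixed-time incidence do better?** The Aalen-Johansen estimate is the sum, over inclusion times up to t, of S(t−) × inclusions / number at risk, where S is the probability of being alive and not yet in a trial. In a simulation with entry possible only from year 2, median survival 6 years and 18 years of uniform accrual, the true 5-year value was 21.3%. Aalen-Johansen gave 21.2%; a simple 5-year share with everyone in the denominator gave 17.3%.

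**4. If the trial-entry rate changes over calendar time.** Censoring is then no longer independent and the pooled estimate drifts (cohort eventual share again 30%):

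- *Fourfold rise in 2005, OS 5, uniform accrual:* estimates 8.7 / 17.0 / 24.0% at 2, 5 and 10 years against true 8.8 / 17.6 / 25.1%; crude share 24.1%. Over 36 rising-rate scenarios the error was at most 0.5, 1.8 and 3.2 points at the three times, on the low side.
- *Fourfold fall in 2012, OS 5, rising accrual:* 10-year estimate 30.6% against true 27.2%, 3.4 points too high.
- *Fourfold fall in 2005, OS 5, uniform accrual:* 28.7% against 27.2%, 1.5 points too high.

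**5. Comparison by period (1990–2004 against 2005–2018).** With a fourfold rise in 2005, OS 5 and rising accrual, eventual access is 22.3% and 32.8%, but the crude shares are 21.4% and 20.6%, in the wrong order. The 5-year incidence, 10.0% and 21.1%, has the right order. Crude counts were lower in the later period in 25 of the 36 scenarios although eventual access was higher there. All 36 assume a rising entry rate.

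**The case against.** The plan states its cut-off and will report median follow-up, so a descriptive share from it is already, by implication, a figure as of that date. It names no estimator and does not promise lifetime access. This stands: the crude share is valid for what it observes and is complete for patients followed to death. What is missing is a label and a measure that allows for unfinished follow-up; a median follow-up helps the reader judge maturity but adjusts nothing.

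Calendar time is not wholly ignored either. The descriptive data include dates, and these data feed the logistic models for type of treatment received. But the plan does not say whether trial inclusion counts as a treatment type, and a logistic model on an ever/never outcome has the same follow-up problem.

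The incidence also has limits. It needs a date that the Methods list does not name for trial inclusion, and the data dictionary it cites is not in the documents. Patients registered some time after metastasis would need delayed entry. The trial item is listed under the metastatic setting, so trials joined earlier, for instance in the adjuvant phase, may be missed. These points are accepted and shape the fix.

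Three stronger readings should be resisted:

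- *The crude share understates national access.* Entry requires a reference centre and database registration. If such patients join trials more often, the share could overstate national access.
- *The pooled incidence can only err low.* That follows only if entry rates rise; with falling rates it errs high.
- *The plan says trial access increased.* The Rational says that changes in drug discovery affected strategies, notably through access to trials, and gives no direction.

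**Conclusion.** The point holds for the registered cohort, provided inclusions are correctly recorded and the proportion is computed as a crude ever/never share, which is the natural reading of the plan. That share is a lower bound for whole-course inclusion. The direction is arithmetic. The size is not in the documents: about 1 to 15 points below an assumed 30% eventual share, depending wholly on assumed entry timing, survival and accrual. A competing-risk incidence at fixed times is a better measure of access than the crude share, although it answers a narrower question. No hypothesis or decision depends on the figure, so this is a cheap improvement the sponsor could make, not a flaw that undermines the study.

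**What to change.** Add to the Statistics section, in substance:

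- The number and percentage of all included patients with a trial inclusion recorded by 31 December 2018 will be reported as 'observed by the cut-off', beside the median follow-up.
- Where a trial-entry date is held, or the trial flag can be linked to a molecule start date, the Aalen-Johansen cumulative incidence of first trial inclusion in the metastatic setting will be added. It runs from diagnosis of metastases, with death as competing event and censoring at last contact, at fixed times (for example 2, 5 and 10 years) with 95% confidence intervals. It will be described as access by that time, not lifetime access.
- The number of undated inclusions will be reported and their effect bounded in a sensitivity analysis, for example by placing them all at the earliest and then all at the latest possible date. They will not be silently dropped or counted as non-events.
- If registration dates show late registration after metastasis, delayed entry will be used.
- Any display by diagnosis period will use this incidence, not crude counts.

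**Cost.** The label is one sentence and needs no new data. The incidence is one standard procedure, but it depends on a linkable date that the Methods section does not list explicitly. It covers the metastatic phase only and is less precise by period. If access changed over calendar time, the pooled late-time value can be a few points too low or too high, according to a direction of change that the documents do not give.

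### Do the two sentences defining time to next treatment leave it open whether a focal procedure ends the interval?

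*Combined protocol and SAP*

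**What the plan says.** The TNT bullet under Survival data (Material and Methods) has two sentences. The first sets the interval: "the time from the systemic treatment onset to the next treatment or death due to any cause, whichever came first". The second sets the censoring rule: "When neither death nor new systemic therapy is observed, TNT is censored at the date of last patient contact".

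The Descriptive data list in the same section places drugs and local procedures under one heading: "Treatment in the metastatic setting : molecule used (start and stop date, best RECIST response), locoregional treatment performed, inclusion in a clinical trial". The Rational section explains why local procedures matter in this disease: "The use of focal treatments such as surgery or interventional radiology with mini invasive procedure of oligometastasis is also being proposed in some cases".

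TNT is a secondary objective and is used twice in the Statistics section. It is an outcome of regression models ("Prognostic factors of TNT and OS will be identified using Cox proportional hazard models") and one side of a correlation ("The correlation between TNT and OS will be evaluated at each of the four first-lines of metastatic chemotherapy"). No sentence in the documents says outright whether a focal procedure on its own ends TNT.

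**The concern.** An event rule and its censoring rule should be complements: whatever does not count as an event leads to censoring, and nothing falls under both. Here the event term is unrestricted and the censoring term is limited to systemic therapy. The plan's own vocabulary calls surgery and interventional radiology treatments, so a focal procedure seems to satisfy the first sentence without satisfying the second.

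If two analysts took different sides, they would give some patients a different status or a different event date. The disagreement could recur at each of the four lines in the correlation analysis, and it would concern patients whose focal treatment the study sets out to describe. There is also a modelling consequence. The Statistics section takes the descriptive data as model variables, and these include locoregional treatment. Under the literal reading, that candidate covariate would also form part of the outcome.

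**Working it through.** The plan states no TNT estimate, event count or sample size, so there is no figure to reproduce. The check is first on the text, then an illustration on assumed values.

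**Step 1: where the two readings differ.**

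| Course after starting a drug | Any treatment ends TNT | Only systemic therapy ends TNT |
|---|---|---|
| New drug or death, no earlier procedure | Event at new drug or death | Same |
| No procedure, no new drug, alive | Censored at last contact | Same |
| Procedure, then new drug or death | Event at procedure | Event at new drug or death |
| Procedure, no new drug, alive | Event at procedure | Censored at last contact |

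Only the last two rows differ, and only the last changes the event status.

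**Step 2: which reading the text supports.**

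- The clock starts at a systemic drug, so the next item in that series is naturally another systemic drug.
- The censoring sentence is in the same bullet. The complement of its condition is death or new systemic therapy, which supplies the event rule in full.
- The correlation analysis counts lines of drug treatment. An interval ended by a procedure while the same drug continued would not correspond to a line.
- The shared heading in the Descriptive data list groups variables to collect. It also covers trial inclusion, so it is not a definition of what ends TNT.
- That list gives start and stop dates for each molecule and no date for locoregional treatment. From the listed variables, an event at the procedure could not be dated.
- The systemic reading keeps locoregional treatment out of the outcome, which suits its use as a model variable.

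**Step 3: what the rival reading could do, on assumed values only.** Assume constant hazards. Let *r* be the rate of focal procedures and *k* the censoring rate, each divided by the rate of new drug or death.

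- Share censored under the systemic rule = k/(1+k). For k = 0.25, 0.5 and 1 this is 20%, 33% and 50%.
- Share with opposite status = r/(1+r+k) × k/(1+k).
- Share with a different date only = r/(1+r+k) × 1/(1+k).

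Example, r = 0.10 and k = 0.25: 0.10/1.35 = 0.0741. Opposite status is 0.0741 × 0.20 = 1.48%; date only is 0.0741 × 0.80 = 5.93%.

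| r | Opposite status (k = 0.25, 0.5, 1) | Date only (k = 0.25, 0.5, 1) |
|---|---|---|
| 0.05 | 0.77%, 1.08%, 1.22% | 3.08%, 2.15%, 1.22% |
| 0.10 | 1.48%, 2.08%, 2.38% | 5.93%, 4.17%, 2.38% |
| 0.25 | 3.33%, 4.76%, 5.56% | 13.33%, 9.52%, 5.56% |

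Under the same constant hazards, if focal procedures were a share *f* of all first TNT-ending occurrences, the median under the broad reading would be (1 − f) times the median under the systemic reading: 5%, 10% or 20% shorter for f = 5%, 10% or 20%. The documents give none of *r*, *k* or *f*. These numbers show what the assumptions imply and are not estimates for this cohort.

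**The case for a change.** The best case for a change is that probable intent is not a written rule. The two terms differ on the page, the example patient is classified in two ways, and correcting the phrase would cost almost nothing. The variable list refers to a data dictionary that is not part of these documents. If it holds procedure dates, the broad reading could be run after all, and with frequent focal treatment the median could shift noticeably, as Step 3 shows.

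Part of this stands. The wording is loose, matching terms would be tidier, and the argument from missing procedure dates rests on the listed variables only. It does not stand as a reason to amend the plan. The other grounds in Step 2 do not depend on the dictionary, and they all lead to the definition that a correction would write in. For the ambiguity to alter a result, an analyst would have to set aside the adjacent censoring sentence and the by-line analysis in favour of the unqualified words in the first sentence.

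**Conclusion.** No change is needed. This is a loose phrase that the next sentence completes: TNT ends at the next systemic therapy or death, and a focal procedure alone does not end it. Under that reading, clearer wording changes no patient's status or date, and so no TNT estimate, Cox model or correlation.

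The conclusion rests on the analyst reading the two sentences together and in line with the Statistics section. If the broad reading were used instead, TNT results could differ by an amount the documents do not allow one to derive. Nothing in the documents shows bias in any prognostic factor. The primary objective is descriptive, and overall survival and the proportion included in a trial do not use the TNT definition.

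### No OS origin is stated for the line-by-line TNT–OS correlation; under the only definition given, OS at lines 2 to 4 includes time survived before the line began

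*Combined protocol and SAP*

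**What the plan says.** The combined protocol and SAP defines both endpoints under Material and Methods, Survival data.

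- **TNT:** "TNT defined as the time from the systemic treatment onset to the next treatment or death due to any cause", whichever came first. Its origin therefore moves with the line.
- **OS in the metastatic setting:** "defined as the interval between the diagnosis of metastatic disease or the first-line systemic therapy onset and the time of death". The censoring rule is general: "When death is not observed, OS is censored at the date of last patient contact".

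The Statistics section then plans: "The correlation between TNT and OS will be evaluated at each of the four first-lines of metastatic chemotherapy", using Spearman's coefficient. On estimation it says: "We will use a reviewed copula-based approach that introduces an iterative multiple imputation method for the estimation of the correlation coefficient". Neither sentence says from which date OS is counted.

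The only other survival origin is in the logistic model, which looks for factors associated "with the probability of survival 5 years after the diagnosis of metastases". It is not line-specific. The Cox models for OS name no origin.

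**The concern.** TNT at line 2, 3 or 4 starts at that line. OS, by the only definition available, starts at metastatic diagnosis or at the start of first-line therapy. An analyst who follows the text literally would correlate a duration that begins late in the disease with one that began one, two or three lines earlier. The second duration includes time that every patient in the analysis has by construction already survived. The resulting coefficient does not describe how TNT at that line relates to survival from that line.

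Another analyst could reasonably count OS from each line's start and report a different coefficient under the same label. The plan does not decide between the two.

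The *or* in the OS definition leaves a second choice open, for the OS Cox models and for the line-1 correlation. Only the 5-year model fixes its origin.

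**Working it through.** The plan gives no expected correlation, event count or line duration, so it has no figure to reproduce. The check has a definitional part, which needs no assumptions, and an illustrative part, in which every input is assumed.

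**1. Origins side by side**

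| Quantity | Origin in the document | Moves with the line? |
|---|---|---|
| TNT at line k | start of line k | yes |
| OS | metastatic diagnosis, or start of line 1 | no |
| OS for the correlation at line k | not stated | – |

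**2. Decomposition**

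For a patient who starts line k:

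OS from start of line 1 = P_k + OS_k, and OS_k = TNT_k + S_k

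Here P_k is the time from the start of line 1 to the start of line k, OS_k is survival from the start of line k, and S_k is survival after the next treatment starts (zero if the patient dies on line k). P_1 = 0, and P_k > 0 for k = 2, 3, 4. With metastatic diagnosis as origin, the gap from diagnosis to line 1 is added at every line, including line 1.

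**3. Share of OS already elapsed (scenario A)**

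Assumed: mean line durations 24/10/6/5 months; 10/20/30/50% of lines 1 to 4 end in death; mean residual survival after line 4 of 6 months; independent lines.

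- Line 4: P = 24 + 10 + 6 = 40; mean OS_4 = 5 + 0.5 × 6 = 8; share 40/48 = 83%.
- Line 3: P = 34; mean OS_3 = 6 + 0.7 × 8 = 11.6; share 34/45.6 = 75%.
- Line 2: P = 24; mean OS_2 = 10 + 0.8 × 11.6 = 19.28; share 24/43.28 = 55%.

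**4. Spearman coefficients, scenario A** (simulation, 400,000 patients, exponential durations, no censoring)

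| Line | As written (from line 1) | From start of line k | Difference |
|---|---|---|---|
| 2 | 0.36 | 0.65 | 0.29 |
| 3 | 0.22 | 0.62 | 0.40 |
| 4 | 0.19 | 0.71 | 0.52 |

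**5. Effect of dependence between a patient's lines**

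The table gives line-specific minus as-written coefficients when a log-normal patient effect is shared across lines. Ranges cover scenario A and scenario B (10 months per line), with deaths ending 10/20/30/50% or 30% of each line.

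| Log-SD of patient effect | Line 2 | Line 4 |
|---|---|---|
| 0 | 0.07–0.29 | 0.38–0.53 |
| 1.0 | 0.02–0.13 | 0.18–0.22 |
| 2.0 | 0.01–0.05 | 0.07–0.09 |

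With log-normal durations (log-SD 1) and latent correlation 0, 0.5, 0.7 or 0.9 between lines, the difference over lines 2 to 4 runs from 0.07 to 0.50, −0.03 to 0.15, −0.06 to 0.07, and −0.13 to 0.01 respectively.

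A separate set of 12 scenarios used median durations 24/8/5/4, 12/8/5/4 or 6/6/6/6 months, 20% or 40% deaths per line, median survival of 3 months after line 4, and log-SD 0 or 0.5. The as-written coefficient was lower by 0.03–0.38 at line 2, 0.12–0.47 at line 3 and 0.31–0.62 at line 4. These runs cover low dependence only.

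**6. What the line-specific origin does not cure**

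Since OS_k = TNT_k + S_k, the coefficient is positive even when TNT_k and S_k are unrelated. In scenario B with independent lines and 10/20/30/50% deaths, lines 1 to 4 give 0.42/0.43/0.44/0.43 as written and 0.42/0.50/0.63/0.85 line-specific. That upward trend reflects only the growing share of OS_k that TNT_k makes up. The line-4 value falls to 0.71, 0.56 or 0.49 if mean residual survival after line 4 is 12, 24 or 36 months instead of 6.

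**7. The two origins in the *or***

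Using metastatic diagnosis instead of the start of line 1 lowers the coefficient by 0.00–0.03 for an assumed mean gap of 3 months and by 0.02–0.14 for 12 months (log-SD up to 1.0).

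**8. A companion measure free of the overlap**

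Correlating TNT_k with S_k among patients who reach the next line removes the shared component. Its true value at line 1 in scenario A is 0.00, 0.20 and 0.47 for log-SD 0, 0.5 and 1.0. Its censoring depends on TNT, because remaining follow-up is total follow-up minus TNT. With follow-up uniform over 0–120 months, censoring after the start of line 2 is 15% in the shortest-TNT third and 30% in the longest (log-SD 0.5), or 12% and 36% (log-SD 1.0). Using observed deaths only would give 0.07 instead of 0.20, and 0.26 instead of 0.47.

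**The case against.** The strongest reply is that this is missing wording, not a demonstrated error. An analysis described as being done at each line, with TNT starting at that line, reads naturally as using line-specific OS. The document also never states what the correlation is for; relating TNT at line k to total metastatic survival is a possible, if less natural, descriptive question. The large contrasts come from independent lines. Under strong dependence the two versions nearly agree or swap order, and the documents do not say which regime applies. The planned copula and imputation estimator was not simulated. The *or* may be deliberate, for example as a fallback for patients without systemic therapy. The overlap between TNT and OS is a separate matter that a new origin does not remove. The correlation is not among the legible objectives.

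Much of this stands. The direction and size in the real data are unknown, the line-specific reading may be intended, and a 3-month gap between the two origins would matter little. It does not answer the main point: OS has an explicit definition, no other is offered for this analysis, and following it at lines 2 to 4 yields a quantity whose origin does not match that of TNT. Where the two coefficients happen to be close, they still answer different questions. The overlap does not weaken the case for aligning the origins, but the limitation has to be stated alongside the correction.

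**Conclusion.** The concern holds. By definition, and without any assumed figure, OS as written includes pre-line survival at three of the four lines in the correlation analysis, and the OS Cox models and the line-1 correlation have two possible origins. How much the coefficients change cannot be read from the documents. Under the assumed inputs, the line-specific coefficient ranges from about 0.5 higher, when lines are independent, to 0.13 lower, when log-normal durations are very strongly correlated (the separate low-dependence runs reach 0.62 higher at line 4). Apart from the companion figures, these values assume no censoring.

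The SAP should be changed on this point, but its reach is limited: the primary descriptive objective is untouched, and the correlation is not a legible listed objective.

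**What to change.** In the Survival data and Statistics sections:

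1. For the correlation at line k, define OS from the onset of line k to death, among patients who start line k, with censoring at last contact as now.
2. Name one origin for the main OS and Cox analyses. Metastatic diagnosis would match the 5-year model; what matters most is that one is named.
3. State that TNT is a component of OS, so coefficients are positive without any real association and can differ between lines for that reason alone, and that differences between lines will not be interpreted from them.
4. Optionally, as a sensitivity analysis, report the correlation of TNT with survival after the next treatment starts. Note that it covers only patients who reach the next line and that its censoring depends on TNT, so the imputation method must be shown to handle this.

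The cost is a few sentences and minor programming. The dates of metastatic disease, the start and stop of each molecule and the latest status are already collected. The data list records molecules with dates and does not mention line numbers, so lines may have to be derived, but TNT by line already requires that. Restricting line k to patients who start it loses no one, since TNT at line k is defined only for them.
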